18.1.2 Secondary Endpoints: Composite clinical score

A composite clinical score in RELAX will be based on a ranking of all participants. All participants will be ranked sequentially with ranking stratified in one of three tiers based on:

1) Death (lowest tier)

The ranking within this tier is based on time to death from randomization date. The person with the shortest time from randomization to death is given the lowest rank within the tier.

2) Hospitalizations due to cardiovascular (CV) or renal causes (middle tier)

For patients alive, the ranking within this tier is based on time to hospitalization from randomization date. The person with the first cardiovascular or renal cause hospitalization will be given the lowest rank within the tier. Cardiovascular causes defined as initial primary cause for hospitalization as HF, acute coronary syndrome, cerebrovascular accident, peripheral vascular disease, arrhythmia or syncope. Renal causes defined as initial primary cause for hospitalization, renal failure or hyperkalemia.

3) Change in MLWHFQ from baseline (highest tier)

For patients without an event meeting the first two criteria, the person with the least favorable change in MLWHFQ is given the lowest rank within this tier. Patients with an equal change in the MLWHFQ will receive an equal ranking.

The use of three tiers within the ranking reflects the greater adverse impact of death or CV hospitalization on clinical status without an arbitrary assignment as to the relative value of these events in relation to changes in quality of life.

As was the case with the primary endpoint, we have no data relevant to the composite clinical endpoint in this population. However, Smith et al ⁷ described functional status changes over 6 months in a population of 200 heart failure patients with preserved ejection fraction. In this population, 13% of subjects died, 27% declined in functional status, 50% maintained functional status and 10% improved. With 190 patients with complete data and an assumption of a proportional odds model for the multinomial response (Agresti)¹¹⁷ we would have 87% power to detect a proportional odds shift of 3.0 and 73% power to detect a proportional odds shift of 2.5^{118} . We would likely have more power with the rankordered data. Assuming approximately 10% missing data and an analysis sample size of 190 patients, we have 80% power to detect a statistically significant difference if P(X<Y) = 0.65 where P(X<Y) is the probability that a randomly selected patient in the sildenafil group has a better outcome rank than a randomly selected control group patient.

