18.2 Analysis Policies

A statistical analysis plan will be completed before the data are analyzed in an unblinded fashion. Due to clinical interest in departures from both sides of the null hypothesis, all test statistics will be twosided. The trial results will be reported according to guidelines specified in the CONSORT statement^{121,122}. A flow diagram describing screening, recruitment, randomization, dropout, and vital status will be included in the primary manuscript. Adverse events and efficacy data will be presented by the two treatment groups. Adherence, dropout, and lost-to-follow-up will be carefully examined across the two treatment groups. Analyses of safety will be based on data from all randomized patients who received at least 1 dose of study drug. All primary analyses will be based on intent-to-treat (ITT) principles using all randomized participants.

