18.2.1 Controlling Type-I Error

The primary endpoint of change in peak VO2 from baseline to 24 weeks will be evaluated at the twosided 0.05 level. A conservative approach will be taken with the multiple analyses on key clinical subgroups. For subgroup analyses, a significance level of 0.001 will be required for statistical significance. Thus, subgroup analyses will be considered exploratory unless the p-value from an interaction test is smaller than 0.001.

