18.6 Specification of the Secondary Analyses

A Wilcoxon test will be used to calculate the P(X<Y) and the p-value for the clinical composite score endpoint. Multivariate rank-ordered data will be analyzed according to the worst-rank approach of Lachin¹²³. A mixed model repeated measures (MMRM) analysis will be used to compare differences in the slope of peak VO2 and 6MW distance across the two treatment groups¹²⁴. Contrast estimates of differences in slopes of treatment by time (along with confidence intervals) will be used to estimate the treatment effect. The validity of this model in terms of meeting modeling assumptions will be assessed via standard modeling diagnostics and goodness-of-fit measures. Based on the MMRM framework, missing peak VO2 and 6MW distance data will not be imputed. Sensitivity analyses will be conducted using an inverse probability weighted method to account for missing data¹²⁵.

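### The three power figures for the composite clinical score do not follow from the stated 190 patients: they understate power by 11 to 18 points and fit a total of about 115

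*Protocol*

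**What the plan says.** Section 18.1.2 borrows a six-month outcome distribution from a cohort of 200 heart failure patients with preserved ejection fraction: "13% of subjects died, 27% declined in functional status, 50% maintained functional status and 10% improved". It then gives two sets of power figures, both for 190 patients.

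- **Four-category model.** "With 190 patients with complete data and an assumption of a proportional odds model for the multinomial response", the text says "we would have 87% power to detect a proportional odds shift of 3.0 and 73% power to detect a proportional odds shift" of 2.5.
- **Rank score.** "Assuming approximately 10% missing data and an analysis sample size of 190 patients", the text says "we have 80% power to detect a statistically significant difference if P(X<Y) = 0.65".

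Between the two it remarks that the ranked data would probably give more power than the categories.

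The planned analysis is in section 18.6: "A Wilcoxon test will be used to calculate the P(X<Y) and the p-value for the clinical composite score endpoint". Section 18.2 says "all test statistics will be twosided". Section 6 gives 1:1 randomization. A significance level is stated only for the primary endpoint, in section 18.2.1: "The primary endpoint of change in peak VO2 from baseline to 24 weeks will be evaluated at the twosided 0.05 level".

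**The concern.** An odds ratio of 3.0 with 95 patients per arm is a large effect, and 87% power looks low for it. The three statements can be checked from inputs printed in the protocol, apart from the significance level.

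The composite is the first secondary endpoint listed, and clinical status stands beside exercise capacity in the trial's stated hypothesis. These figures are the protocol's only account of what effect on clinical status the trial could be expected to find. If they are too pessimistic, a neutral composite result may be excused as underpowered when the design could in fact have picked up a smaller effect. A follow-on outcome trial, which section 18.1.1 mentions as a possibility, could also start from the wrong benchmark.

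**Working it through.** **Inputs**

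- N = 190 in total, 95 per arm (18.1.2; 1:1 from section 6).
- Reference distribution, worst to best: 0.13, 0.27, 0.50, 0.10 (18.1.2), taken as the control arm.
- Effects: odds ratio 3.0, odds ratio 2.5, P(X<Y) = 0.65 (18.1.2).
- Wilcoxon test (18.6), two-sided (18.2).
- Level 0.05, so z = 1.96. This is an assumption, carried over from the primary endpoint.

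**Proportional-odds figures**

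Power = Φ( ln(OR) × √V − 1.96 ), with V = (N/12) × (1 − Σ p̄³), where p̄ is the average of the two arms' category probabilities.

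*Odds ratio 3.0*

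- Control cumulative probabilities are 0.13, 0.40 and 0.90, with odds 0.149, 0.667 and 9.
- Dividing the odds by 3 gives treated cumulative probabilities 0.047, 0.182 and 0.750, so the treated categories are 0.047, 0.134, 0.568 and 0.250.
- The averages are 0.089, 0.202, 0.534 and 0.175, and Σ p̄³ = 0.167.
- V = (190/12) × 0.833 = 13.19, and √V = 3.632.
- Power = Φ(1.0986 × 3.632 − 1.96) = Φ(2.03) = **97.9%**, against 87% stated.

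*Odds ratio 2.5*

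- The treated categories are 0.056, 0.154, 0.572 and 0.217, and Σ p̄³ = 0.168.
- V = 13.17, and √V = 3.629.
- Power = Φ(0.9163 × 3.629 − 1.96) = Φ(1.365) = **91.4%**, against 73% stated.

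Simulated Wilcoxon tests with 95 per arm give about 97.4% and 91%. Tie-corrected normal approximations to the Wilcoxon test, and using the listed distribution as the treated or the average arm instead, move the results only within 96.8–98.5% and 89.6–93.0%.

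**Rank-score figure**

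Noether's formula: power = Φ( √(3N) × |P − 0.5| − 1.96 ).

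- N = 190: √570 = 23.87, and Φ(23.87 × 0.15 − 1.96) = Φ(1.62) = **94.8%**, against 80% stated. Simulation gives 95–96%.
- Effect detectable at 80% power: 0.5 + (1.96 + 0.842)/23.87 = **0.617**, not 0.65.
- In the proportional-odds formula, 80% power at N = 190 is reached at an odds ratio of about 2.17.

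**What would reproduce the stated figures?**

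The same formulas under other settings:

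| Setting | OR 3.0 | OR 2.5 | P(X<Y) = 0.65 |
|---|---|---|---|
| Stated | 87% | 73% | 80% |
| N = 190, two-sided 0.05 | 97.9% | 91.4% | 94.8% |
| N = 190, two-sided 0.01 | 92.1% | 77.3% | 84.3% |
| N = 190, two-sided 0.005 | 88.2% | 69.8% | 78.1% |
| N = 161 (215 × 0.75, the primary's 25% loss), 0.05 | 95.7% | 86.4% | 90.9% |
| N = 95, 0.05 | 80.6% | 65.2% | 71.6% |
| N = 115, 0.05 | 87.4% | 73.5% | 79.6% |

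Solving for N at 0.05 one figure at a time gives 113.7, 113.8 and 116.3. Across the methods tried, the sizes that bring all three within 2 points run from 111 to 122. One-sided testing raises power and widens the gap.

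**Check on a neighbouring figure**

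Section 18.1.3 states 90% power for 33 m with SD 70 m and 190 patients. Φ(33 / (70 × √(2/95)) − 1.96) = Φ(1.29) = 90.1%. That figure reproduces at 190 patients with two-sided 0.05.

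**The case against.** The strongest objection is that the level is assumed. Section 18.1.2 names none, and 0.05 is fixed only for the primary endpoint. Power depends on size and level together, so a stricter level could stand in for a smaller sample. At two-sided 0.01, one version of the tie-corrected Wilcoxon approximation gives about 89% and 74%, close to the stated 87% and 73%. This stands as a caution but does not rescue the paragraph. At 0.01 the rank-score figure is 84%, not 80%. Bringing all three figures within 2 points at N = 190 takes an unusual level of roughly 0.0055 to 0.0075 combined with particular variance choices, and nothing in the protocol supports such a level. The 6-minute walk figure reproduces at 190 with 0.05.

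It also stands that about 115 patients is an inference. No section mentions that number, and the matching size shifts somewhat with the method.

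The remark that ranked data would have more power does not explain the gap. The 87% and 73% are too low for the four-category model itself, and the 80% is already a rank-test figure.

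Finally, the error is conservative. The trial's size rests on peak VO2, no decision rule uses these numbers, and a neutral result should be read from its estimate and uncertainty rather than from planned power. All of that is true. It limits the consequence but does not make the figures right.

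**Conclusion.** The concern holds. With 190 analysed patients, the quoted distribution, 1:1 allocation and two-sided 0.05, power is about 98% for an odds ratio of 3.0, 91% for 2.5, and 95% at P(X<Y) = 0.65. The stated figures are too low by about 11, 18 and 15 points. Put as the chance of missing the effect, the text implies 13%, 27% and 20%, where the design gives about 2%, 9% and 5%.

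The result assumes the 0.05 level and takes the borrowed four-category distribution as given, as the protocol does. The choice of approximation does not matter at this scale. The three figures agree with one another at about 115 patients, so one wrong input common to all three is the likeliest explanation, but the document does not show its source.

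This is a should-fix correction to planning text for a secondary endpoint. It affects neither the trial's size nor its type I error.

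**What to change.** In section 18.1.2, confirm the size and significance level behind the calculation and print the level. If 190 patients and two-sided 0.05 are intended, replace the three numbers: about 98% power for an odds ratio of 3.0, about 91% for 2.5, and 80% power at P(X<Y) = 0.62 (95% at 0.65). If losses like the 25% allowed for the primary endpoint are expected here too, add that 161 patients reach 80% power at P(X<Y) = 0.627. If another size or level was really meant, state it in place of 190.

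The cost is a text correction to one paragraph, with no change to sample size, analysis or conduct.

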18.1.3 Secondary Endpoint: 6 Minute Walk Distance

No previous study has characterized the standard deviation of the Δ 6MW in a study population similar to that planned here where DHF patients are studied and strict entry criteria and a screening CPXT are used to minimize enrollment of patients with non-cardiac dyspnea and select for patients who can perform near maximal exercise (RER≥1.0). Recognizing the lack of data relevant to the planned study population, we have based power calculations on the SD for the Δ 6MW observed in the PEP-CHF trial in DHF⁴⁷ (n≈650). In this trial, the SD for the Δ 6MW was ≈70m ([name], personal communication, 2/28/2007) which was similar to the SD used for sample size estimates in the SUPER trial of sildenafil in PH⁶⁸. Further, this was similar to the SD for Δ 6MW observed in a small (SD=80m, n=34) RCT of chronic sildenafil therapy in SHF ([name], personal communication). As above, a range of withdrawal due to death at 6 months was also estimated based on a large RCT in DHF (<2%)⁴⁷ and community based observational studies in DHF (13-16%)^{7,11}.

With the assumed common standard deviation of 70m, an analysis sample size of 190 patients (allowing for 10% missing data) will have 90% power to detect a difference in Δ 6MW of 33m. In the SUPER trial of PDE-5 inhibition in PH, the placebo corrected mean difference in Δ 6MW between treatment groups was approximately 45m⁶⁸. In RELAX, we hypothesize that improvements in exercise capacity will be mediated not only by effects on pulmonary vascular tone, but also by effects on the systemic vasculature, LV and kidney. Thus, the potential for greater benefit in DHF than in PH exists.

18.1.4 Secondary Endpoint: MRI assessment of LV mass

Given the very high reproducibility of LV mass assessment by MRI, MRI of the entire RELAX cohort will not be needed to provide excellent power to detect clinically relevant changes in LV mass. A single center study assessed the reproducibility of measurements of LV mass by MRI and reported that the mean difference between repeat MRI measurement of LV mass was -1.1 ± 4.2 g (LV mass index -0.6 ± 2.1 g/m²) in 20 normal persons and -2.4 ± 8.4 g (LV mass index -1.3 ± 4.0 g/m²) in 20 patients with LVH¹¹⁹. These inter-study reproducibility values were similar to several other small studies and markedly better than inter-study reproducibility of echocardiography. The "4-E study" ¹²⁰ was a multicenter study using MRI assessment of LV mass in patients with hypertension. Power calculations for the 4-E study assumed a standard deviation of 24g in the change in LV mass from baseline (3 x the SD reported in the Grothues study).

Based on these previous studies, enrollment of 132 patients in the "Sinus Rhythm" arm of RELAX would provide 85% power to detect a difference in the change in LV mass of 14.1g between groups with a conservative assumption of 20% missing data and a standard deviation of 24g (see table below).

				Assuming 20% missing data (available data for						
MRI ass	sessment of L	V mass (n=	132)		n=1	06)				
SD	8g	16g	24g	SD	8g	16g	24g			
Difference in	change in LV	mass dete	ctable (g)	Difference in	n change in	LV mass det	ectable (g)			
85% power	4.2	8.4	12.6	85% power	4.7	9.4	14.1			
90% power	4.6	9.1	13.7	90% power	5.1	10.2	15.3			

Other tertiary endpoints: Allowing for 10% missing data, our projected sample size of 215 subjects would provide 85% power to detect an effect size of 0.44 for any of the tertiary endpoints.

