12. BASELINE EVALUATIONS AND RANDOMIZATION

12.1 Evaluations Performed During the Baseline Period

The following studies will be performed during the baseline period prior to randomization and starting study drug. Please see section 13 for a detailed description of these procedures as well as the schedule of evaluations as outlined in Appendix 22.1.

- 1. Limited Doppler echocardiography
- 2. Cardiac Magnetic Resonance Imaging (MRI) (Patients in sinus rhythm only at enrolling sites with MRI access)
- 3. Phlebotomy for Biomarkers
- 4. Metabolic stress test (Screening study may be submitted to the CORE CPXT laboratory as the baseline study if patient meets entry criteria)
- 5. Six minute walk test
- 6. Minnesota Living with Heart Failure Questionnaire
- 7. Creatinine
- 8. Electrocardiogram
- 9. Clinical history
- 10. Physical examination which will include simple bedside hearing assessment (ability to hear examiner's fingers rubbed together in front of each ear).

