18. STATISTICAL CONSIDERATIONS

18.1 Sample Size and Power Considerations

18.1.1 Primary endpoint: Change in peak VO₂ (\triangle VO₂)

No previous study has characterized the standard deviation of the ΔVO_2 in a study population similar to that planned here where DHF patients are studied and strict entry criteria and a screening cardiopulmonary exercise test (CPXT) are used to minimize enrollment of patients with non-cardiac dyspnea and select for patients who can perform near maximal exercise (RER≥1.0). Patients who are unwilling or unable to perform at this level of exercise will not be eligible for enrollment. This requirement will reduce variability in both the primary endpoint (Δ peak VO₂) and the secondary endpoint measuring submaximal exercise (\alpha 6MW). Recognizing the lack of data relevant to the planned study population, we have based power calculations on the SD for the ΔVO_2 observed in randomized clinical trials (RCT) in SHF where ΔVO₂ was a primary (SD=2.7 ml/kg/min)¹¹¹ or secondary (SD≈2.7 ml/kg/min) ^{112,113} endpoint and on limited RCT data in DHF⁵⁰ (SD=1.3 ml/kg/min; [name], personal communication). A range of withdrawal due to death at 6 months was also estimated based on a large RCT in DHF (<2%)⁴⁷ and community based observational studies in DHF (13-16%)^{7,11}.

Power	85% Power			90% Power			analysis indicates that a sar	
	TE = 1.0 ml/kg/min	nin ml/kg/min	ml/kg/min ml/	TE = 1.0 ml/kg/min 172	TE = 1.2 ml/kg/min 120	TE =1.5 ml/kg/min	1.2 ml/kg/min in ΔVO_2 with	
SD=2.0	146					78		
SD=2.5	228	158	102	266	186	120	SD of ΔVO_2 =2.5 ml/kg/min. account for up to 25% mis	
SD=3.0	326	228 146	382	266	172	data, the projected sample s		
							is approximately 215 patients In patients with SHF, a si dose of sildenafil resulted in	

The relationship between power, effect size (mean difference in ΔVO_2) and SD of the ΔVO_2 using a two sample t-test and a two-sided alpha of 0.05 is shown in the table assuming 85% and 90% power. This

dose of sildenafil resulted in statistically significant increases in

TE=treatment effect (difference in Δ in peak VO2); SD = standard deviation of Δ in peak VO2

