18.3 Randomization

A permuted block randomization scheme will be created with varying block sizes stratified by the presence or absence of atrial fibrillation. Enrollment of patients with atrial fibrillation is planned to be limited to 58 patients (30% of study population). Once 58 patients with chronic atrial fibrillation have been enrolled, the DCC and DSMB will review the characteristics (atrial fibrillation versus sinus rhythm) of all patients enrolled and will increase this limit if needed to insure adequate enrollment to address the primary endpoint. Once a patient has completed the screening and baseline period and evaluation for inclusion/exclusion criteria, the randomization process will begin. Patients will be randomized to receive one of the 2 treatment regimes with equal probability (1:1), via a Web based system (WebEZ). On the day of randomization, after the patient has successfully met all inclusion and exclusion criteria, the investigator or designee will log into the on-line WebEZ randomization system to obtain the assigned kit randomization numbers for the patient. The WebEZ system will also be used for re-supply of the site.

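### Section 18.1.4 claims 85% power at effect size 0.44 for every tertiary endpoint; this fails for the MRI vascular endpoints and is unsupported for exercise time and VAT

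*Protocol*

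**What the plan says.** The last paragraph of section 18.1.4 covers the tertiary endpoints other than LV mass. It starts from 215 subjects with 10% missing and says this "would provide 85% power to detect an effect size of 0.44 for any of the tertiary endpoints".

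Other parts of the Protocol bear on that claim:

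- **MRI population.** Section 12.1 restricts cardiac MRI: "Patients in sinus rhythm only at enrolling sites with MRI access". Section 14.2.4 excludes atrial fibrillation (AF) patients from baseline and follow-up MRI. It obtains aortic thickness and distensibility from MRI and lists Ea and SVR among the MRI-derived indices. Sections 2 and 6 make all four part of tertiary endpoint 6.
- **MRI sample size.** The table just above the claim starts from 132 sinus-rhythm patients, allows 20% missing, and arrives at 106 with data. At SD 24 g it gives 14.1 g as detectable with 85% power.
- **Primary endpoint.** Section 18.1.1 raises the sample size to about 215 to "account for up to 25% mis"sing data (the extracted text breaks there) on peak VO2.
- **6-minute walk.** In section 18.1.3, "an analysis sample size of 190 patients (allowing for 10% missing data) will have 90% power" for a 33 m difference at SD 70 m.
- **Counts.** Section 18.3 describes AF enrolment as "limited to 58 patients (30% of study population"). Section 18.1.4 is headed as a secondary endpoint, while sections 2 and 6 list LV mass as tertiary.

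**The concern.** One power figure is applied to endpoints measured in different numbers of patients. An endpoint that excludes AF patients cannot have the whole-cohort denominator, and the smaller denominator is printed a few lines above the claim. Exercise time and VAT are read from the test that yields peak VO2, yet they carry a 10% missing allowance while peak VO2 carries up to 25%, with no reason given.

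Section 18.1.1 makes the study of mechanisms a joint aim and says that benefit on key mechanisms may support a larger outcome trial. The vascular MRI measures are part of that evidence, so a reader weighing a neutral result needs to know what effect the trial could have detected.

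**Working it through.** **Method.** Two-sample t-test, 1:1 allocation, two-sided 0.05. Section 18.1.1 states the test and level for the primary endpoint ("sample t-test and a two-sided alpha of 0.05 is shown in the table assuming 85% and 90% power"), and section 18.2 says "all test statistics will be twosided". Applying the same test to the tertiary endpoints is my assumption. With N analysed in total and effect size d, the noncentrality is λ = d√N / 2 with N − 2 degrees of freedom. Power is the probability that the noncentral t exceeds the 0.975 central quantile. The normal approximation gives values within about one percentage point of those below.

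**Step 1: reproduce the plan's figures.**

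- Tertiary: 215 × 0.90 = 193.5; sections 18.1.2 and 18.1.3 use 190. At d = 0.44, power is 86.1% with 193.5 and 85.5% with 190. The stated 85% reproduces.
- LV mass: N = 106, SD 24 g, 85% power gives 14.10 g. The stated 14.1 g reproduces, and 14.1 / 24 = 0.5875 SD.
- 6-minute walk: 33 / 70 = 0.471; with N = 190, power is 89.8%. The stated 90% reproduces.

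**Step 2: apply d = 0.44 to the numbers that fit each endpoint.**

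| Basis | N | λ | Power at 0.44 | Effect size for 85% power |
|---|---|---|---|---|
| Whole cohort, about 10% missing | 190 | 3.03 | 85.5% | 0.437 |
| MRI, protocol count (132 × 0.80) | 106 | 2.27 | 61.2% | 0.588 |
| MRI, AF cap filled at 215 (157 × 0.80) | 126 | 2.47 | 68.8% | 0.538 |
| MRI, AF cap filled, none missing | 157 | 2.76 | 78.2% | 0.481 |
| MRI, no AF patient at all (215 × 0.80) | 172 | 2.89 | 81.8% | 0.460 |
| Exercise test, 25% missing (215 × 0.75) | 161 | 2.79 | 79.2% | 0.475 |

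The 157 is 215 − 58. It applies if the AF cap is exactly filled: fewer AF patients would raise it, and raising the cap, which sections 8.3 and 18.3 permit, could lower it. The 172 row is the ceiling at the protocol's 20% MRI missing rate. Even there, power at 0.44 stays below 85%.

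**Step 3: 6-minute walk sensitivity (SD 70 m, 33 m).** At 25% missing (N = 161), power is 84.4%, and 90% power needs 36.0 m. At 16% missing (215 × 0.84 ≈ 181), power is 88.4%.

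**Step 4: counts.** 58 + 132 = 190. 58 / 190 = 30.5%, whereas 58 / 215 = 27.0%. The AF and sinus-rhythm numbers and the 30% all fit a total of 190, not 215.

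**The case against.** The strongest reply is that the claim is labelled as covering the other tertiary endpoints and comes directly after LV mass has had its own calculation. That stands. A reader might infer that the protocol overstates power for LV mass; it does not. It never attaches 0.44 to LV mass, and its 14.1 g is correct at 106 patients. Nor is the whole of tertiary endpoint 4 limited by MRI, since its matrix markers are blood assays. But the label removes only LV mass. Aortic thickness and distensibility remain inside the claim, as do Ea and SVR as section 14.2.4 derives them. The echocardiogram in section 14.2.5 also yields a stroke volume, so Ea and SVR would escape the point if taken from echo.

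A reader might also infer that the 6-minute-walk power is wrong because peak VO2, measured at the same visits, allows more missing data. The documents do not support that. The 90% follows from its stated inputs. The 25% is an upper allowance for a near-maximal test, and a self-paced walk with rests and mobility aids need not lose as many patients. Section 18.1.3 quotes 13-16% six-month mortality from community studies, which exceeds 10%, but also under 2% from a large trial in this disease. Section 18.6 plans a repeated-measures model for peak VO2 and walk distance, so the complete-case loss in Step 3 is approximate. What remains is that the difference between 10% and 25% is unexplained. It matters most for exercise time and VAT, which come from the same test as peak VO2.

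Finally, these endpoints are exploratory, and neither the trial size nor the primary power depends on them. That limits the weight of the point but does not make the sentence correct.

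**Conclusion.** The claim of 85% power at 0.44 for any tertiary endpoint is wrong for the MRI-derived endpoints other than LV mass. On the protocol's own 106 patients, power is about 61% and the effect detectable with 85% power is about 0.59 SD. On about 126 it is about 69% and 0.54 SD. This rests on the t-test above and on the 20% MRI missing rate; the documents do not say whether that rate also covers sites without MRI.

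For exercise time and VAT the claim is unsupported rather than refuted: power is about 79% if the full peak VO2 allowance is used up, and 85% power then needs about 0.475 SD.

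The 6-minute-walk and LV mass figures stand as arithmetic. The counts of 58, 132 and 30%, and the heading of section 18.1.4, are inconsistencies to tidy. Saying that neutral results would be misread goes further than the documents allow. The narrower point is that the stated benchmark for reading them is wrong for some endpoints.

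**What to change.** - **Section 18.1.4, power claim.** Limit the 0.44 statement to endpoints measured in the whole cohort with 10% missing.
- **Section 18.1.4, MRI endpoints.** State the effect detectable with 85% power on one declared MRI count: 0.59 SD at 106 analysed (from 132 in sinus rhythm), or 0.54 SD at about 126 (from 157). The two bases should not be mixed. Say whether Ea and SVR will come from MRI or echo.
- **Exercise time and VAT.** Use the peak VO2 missing-data allowance (0.475 SD at 161), or give a reason for 10%.
- **Section 18.1.3.** Keep 90% for 33 m at 190 patients. Add as a sensitivity that at 25% missing power is about 84%, and 90% power needs 36 m.
- **Counts and labels.** Reconcile the 58 AF patients, the 132 in sinus rhythm and the 30% with the 215 planned, here and where section 8.3 repeats the cap. Align the heading of section 18.1.4 with the tertiary status of LV mass.

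The cost is revised text in the power section and the enrolment counts. There are no extra patients and no change to the primary analysis.
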